12.8.2 Reporting Requirements

The following events are considered reportable events:

- any serious adverse event that has a causal relationship with the investigational device, the comparator or the investigation procedure or where such causal relationship is reasonably possible;
- b) any device deficiency that might have led to a serious adverse event if appropriate action had not been taken, intervention had not occurred, or circumstances had been less fortunate;
- c) any new findings in relation to any event referred to in points a) and b).

All causality assessments should be made using the guidance in the section above. Only causality level 1 (i.e. "not related") is excluded from reporting. If either the sponsor or the investigator has assigned a higher causality level than "not related", the event should be reported.

12.8.3 Reporting Timelines

The sponsor must report to the CEC and as applicable, to all NCAs where the clinical investigation is authorized to start:

- For all reportable events as described in section 6.4 which indicate an imminent risk of death, serious injury, or serious illness and that requires prompt remedial action for other patients/subjects, users or other persons or a new finding to it: Immediately, but not later than 2 calendar days after awareness by sponsor of a new reportable event or of new information in relation with an already reported event.
 - This includes events that are of significant and unexpected nature such that they become alarming as a potential public health hazard. It also includes the possibility of multiple deaths occurring at short intervals. These concerns may be identified by either the NCA or the manufacturer.
- Any other reportable events as described in section 6.4 or a new finding/update to it: Immediately, but not later than 7 calendar days following the date of awareness by the sponsor of the new reportable event or of new information in relation with an already reported event.

12.9 List of foreseeable adverse events and anticipated adverse device effects, together with their likely incidence, mitigation or treatment

There are currently no adverse device effects associated with the Hemanext RBC Processing System reported in the earlier in vivo and pivotal human trial as reported in the Investigator Brochure. Hemanext RBC Processing System related potential Adverse Device Effects (including potential Serious Adverse Effects) may include, but are not limited to risks related to:

- Lack of sickle cell trait testing of RBC unit before processing and storage in the Hemanext RBC
 Processing System leading to high hemolysis and sickled red blood cells being transfused
 - A false negative on sickle trait testing of RBC unit before processing and storage in the Hemanext RBC Processing System leading to high hemolysis and sickled red blood cells being transfused
- Undetected leak in the HSB inner bag leading to a loss of sterility of the RBC unit. The product labeling is for fluid path sterility only.
- Use of a non-indicated additive solution with the Hemanext RBC Processing System leading to negatively affected quality of RBCs

The incidence is unknown. Mitigation of associated risk is achieved via continuous pharmacovigilance activities conducted during the study.

Well established blood transfusion complications (acute and delayed transfusion related effects) known to occur in medical practice using a conventional method of blood processing and storage will be considered as expected events. These effects are listed below¹⁸:

• Transfusion-associated graft versus host disease

- Transfusion-related acute lung injury (TRALI)
- Post transfusion purpura
- Transfusion-associated circulatory overload (TACO)
- Transfusion-transmitted infection (TTI)
- Allergic reaction
- Transfusion-associated dyspnea (TAD)
- Febrile non-hemolytic transfusion reaction (FNHTR)
- Hypotensive transfusion reaction
- Delayed hemolytic transfusion reaction (DHTR)
- Delayed serologic transfusion reaction (DSTR)
- Acute hemolytic transfusion reaction (AHTR)
- Major cardiac event (MCE)
- Haematoma (bruise)
- Arterial puncture
- Delayed bleeding (re-bleeding)
- Nerve injury/irritation
- Localized infection/inflammation
- Deep venous thrombosis (DVT)
- Arteriovenous fistula
- Compartment syndrome
- Brachial artery pseudo-aneurysm
- Vasovagal reactions

12.10 Assessment, notification and reporting on the use of radiation sources Not Applicable.

13. STATISTICAL METHODS

13.1 Hypothesis

Study is not powered so there is no hypothesis in this clinical investigation.

13.2 Determination of Sample Size

10 burn patients and 10 patients with haematological malignancies, who require transfusion of red cell concentrate and who fulfil all eligibility criteria will be enrolled in this clinical investigation at Haukeland University Hospital.

A total of twenty patients will be sufficient to assess preliminary safety as the rate of transfusion related adverse events is usually low and if unexpected adverse events (any type or grade) should occur, this will be identified.

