	 Transfusion of two units of Red Blood Cells, Leukocytes reduced, O₂/CO₂ reduced (single transfusion course) manufactured with the Hemanext ONE System, combined with PRN standard Red Blood Cells, as applicable. Patient's diary
Control intervention (if applicable):	Not applicable
Number of subjects with rationale:	10 acute burn patients and 10 patients with haematological malignancies, who require transfusion of red cells concentrates and who fulfil all eligibility criteria will be enrolled in this clinical investigation at Haukeland University Hospital.
	A total of twenty patients will be sufficient to assess preliminary safety of O ₂ /CO ₂ reduced RBCs, as the standard rate of transfusion related adverse events is usually low and these expected events are well known. If any unexpected adverse events (any type or grade) should occur, they will be identified as such.
Duration of the investigation:	This clinical investigation is estimated to last for a period of approximately 6 months.
Investigation	Anticipated Start Date: May – June 2022
schedule:	Anticipated End Date: November – December 2022
Investigator(s):	Principal Investigator: [name]
	Address: Haukeland University Hespital [name]
	Haukeland University Hospital, [name]
	Norway
	Phone:
	E-mail:

	Sub-Investigator: [name] Address : Haukeland University Hospital, [name] Norway E-mail:
Investigational Site(s):	This clinical investigation will only involve one single clinical site:
	Haukeland University Hospital [name] Norway
Blood Bank	Oslo: Address: Department of Immunology and Transfusion Medicine Section for Blood processing Oslo University Hospital Ullevål Norway
	Bergen: Address:
	Address: Haukeland University Hospital Department of Immunology and Transfusion Medicine [name] Norway E-mail:
Data Monitoring Committee (DMC)	Membership: Professor of intensive care medicine

	Haukeland University Hospital, Bergen
	Chief of Burns, Plastic and reconstructive surgeon
	Haukeland University Hospital, Bergen
	Pland Pank, Haukaland University Heanital, Person
	Blood Bank - Haukeland University Hospital, Bergen
	Blood Bank - Haukeland University Hospital, Bergen
	Blood Bank - Haukeland University Hospital, Bergen
Statistical considerations:	This clinical investigation is not statistically powered – only descriptive statistical methods will be applied

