9.4 Criteria for withdrawal / discontinuation of subjects

A participant may be discontinued from the study for the following reasons:

- 1. Serious adverse events
- 2. Withdrawal of consent
- 3. Investigator decision
- 4. Death, any cause

Any participant that enrolled in the study can withdraw from the study, effectively withdrawing consent, at any time, for any reason, without prejudice or consequence. Participants are to be informed that they are free to leave the study at any time for any reason without prejudice or consequence in the informed consent document. If a participant withdraws from the study the data collected up through the time of withdrawal (including testing results) will be included within the study database. Withdrawn participants will be replaced in order to meet the sample size requirements of the study.

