13.4.2 Primary Analysis

This clinical investigation is not powered to support a quantitative analysis of the primary endpoint.

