13.4.3 Secondary Analyses

The analysis of quantitative secondary endpoints will be limited to descriptive statistics.

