5.1 Sample Size

A total of twenty patients - 10 burn patients and 10 patients with haematological malignancies will be enrolled in the study. Twenty patients will be sufficient to assess preliminary safety of O2/CO2 reduced RBCs, as the rate of transfusion related adverse events is usually low and if unexpected adverse events (any type or grade) should occur, this will be identified. There are no statistical criteria for choosing twenty patients.

6 Assessments

A schedule of assessments can be found in Appendix A: for Hematological malignancies patient group and Appendix B: for Burn patients Group.

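### A low rate of transfusion-related adverse events is not a reason why twenty patients suffice, and the protocol and SAP text plan no interval showing what 10 or 20 patients can exclude (minor)

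*Protocol*

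**What the plan says.** Three places give the same reason for the sample size of 10 burn and 10 haematology patients.

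- Protocol 13.2: "A total of twenty patients will be sufficient to assess preliminary safety as the rate of transfusion related adverse events is usually low". The sentence goes on to say that any unexpected event would be noticed.
- Protocol synopsis, number of subjects: twenty suffice "as the standard rate of transfusion related adverse events is usually low and these expected events are well known".
- SAP 5.1: "Twenty patients will be sufficient to assess preliminary safety of O2/CO2 reduced RBCs, as the rate of transfusion related adverse events is usually low". The same section then says "There are no statistical criteria for choosing twenty patients".

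The limits of the study are disclosed. The synopsis says that "only descriptive statistical methods will be applied", protocol 13.1 says there is no hypothesis, and protocol 13.4.2 says "This clinical investigation is not powered to support a quantitative analysis of the primary endpoint".

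For reporting, protocol 13.4 plans descriptive statistics and a listing of adverse events (AEs). SAP 7.8.1 (AEs) and 7.8.2 (adverse device effects, ADEs) plan event totals and numbers and percentages of patients affected. SAP 7.1.1 presents results by group and in total, and leaves out the percentage when the count is zero. None of these sections mentions a confidence interval or names the analysis set for the two overview tables. Mock tables are in a separate Data Display Plan.

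**The concern.** The stated reason works against the conclusion drawn from it. The rarer an event, the less likely a small study is to see it, and the less a zero count means.

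The risk lies in how the results are read. There is no comparator (protocol 5.6), and SAP 8.1 removed the historical comparison because the data are not available. The report would show counts from 10 or 20 patients beside a statement that twenty are enough because events are rare. A zero or low count of device-related or transfusion-related events could then be taken as more reassuring than it is. A zero count is also the case in which SAP 7.1.1 prints no percentage and the planned text provides no upper limit.

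**Working it through.** **Inputs.** n = 10 per group and 20 in total (protocol 13.2, SAP 5.1). The event rate is described only as low, and protocol 12.9 gives the incidence of potential device effects as unknown. No alpha, power, margin or precision target is stated.

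**The plan's own figure.** Twenty cannot be reproduced, because there is nothing to derive it from. SAP 5.1 says as much. The check is therefore what 10 and 20 patients can show, assuming that all are transfused, that patients are independent and, for the total, that both groups share one rate.

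**Step 1: chance of at least one event, 1 − (1 − p)^n.** The rates are assumptions.

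| Assumed true rate p | n = 10 | n = 20 |
|---|---|---|
| 1% | 9.6% | 18.2% |
| 2% | 18.3% | 33.2% |
| 5% | 40.1% | 64.2% |
| 10% | 65.1% | 87.8% |

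At 1%, a group of 10 misses the event about 90% of the time and 20 patients miss it about 82% of the time. The chance falls with the rate in both columns.

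**Step 2: rate needed for an 80% chance of at least one event, p = 1 − 0.2^(1/n).**
- n = 10: 1 − 0.2^(0.1) = 14.9%
- n = 20: 1 − 0.2^(0.05) = 7.7%

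**Step 3: rate below which seeing none is the likelier result, p = 1 − 0.5^(1/n).** This is 6.7% for n = 10 and 3.4% for n = 20.

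**Step 4: exact two-sided 95% (Clopper-Pearson) limits.** With zero events the upper limit is 1 − 0.025^(1/n).

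| Events seen | n = 10 | n = 20 |
|---|---|---|
| 0 | 0 to 30.8% | 0 to 16.8% |
| 1 | 0.3% to 44.5% | 0.1% to 24.9% |
| half the patients | 18.7% to 81.3% (5/10) | 27.2% to 72.8% (10/20) |

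The last row matters for the primary outcome, patients with any AE, where a zero count is unlikely.

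**Step 5: denominator.** The number analysed may not be exactly 10 per group. Protocol 9.4 says "Withdrawn participants will be replaced in order to meet the sample size requirements of the study", and 13.4.1 keeps the data of those who withdraw. If this gave 11 or 12 transfused patients per group (an assumption), the zero-event upper limit would be 28.5% or 26.5%. The conclusion does not change, but the interval should use the actual number.

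**The case against.** The best defence is that the rationale is about background noise. If expected reactions are few and well known, an unexpected event or an excess stands out. At an assumed 1% background, two or more events in 20 has probability 1 − (0.99^20 + 20 × 0.01 × 0.99^19) = 1.7%. At an assumed 20% background it is 1 − (0.8^20 + 20 × 0.2 × 0.8^19) = 93%. This stands as an argument about recognising an event once it has occurred. It does not make an event likely to occur among twenty patients, so it does not support sufficiency.

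Other points for the plan also stand, and they lower the severity:

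- The aim is preliminary safety only. The lack of power, of a hypothesis and of a statistical basis for twenty is disclosed, and protocol 5.5 leaves further safety study to later randomised trials.
- The Data Monitoring Committee reviews the first five haematology patients before enrolment continues (synopsis, SAP 4). It also reviews and adjudicates all AEs (protocol 3.6).
- Counts, denominators and full listings are planned, so a reader could derive the intervals.
- The zero-event limits bear on rare related events, not on the any-AE primary outcome.
- The Data Display Plan was not available. The statement that no interval is planned rests on the protocol and SAP text. Mock tables could meet the reporting point but would not repair the rationale.

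**Conclusion.** The concern holds as a minor flaw of rationale and reporting. The low rate should not be given as the reason why twenty suffice. With 10 per group transfused, the study has an 80% chance of seeing at least one event only if the true per-patient rate is about 14.9% in a group (7.7% overall). A zero count leaves rates up to 30.8% in a group (16.8% overall) within the 95% interval. These are thresholds, because the documents give no rate. No test or stopping rule depends on them.

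A reader might infer two stronger points that the documents do not support.

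- *That the study is underpowered or needs more patients.* It makes no powered claim and tests no hypothesis.
- *That reactions to conventional units would vanish from the tables.* Protocol 10.1.1 allows such units, and 12.8.1 rates complications of concomitant treatments outside the plan's requirements as not related. But SAP 7.8.1 has a category for unrelated events, so such a reaction would still be counted there, in the organ-class tables and in the listings. The synopsis also names standard units within the intervention, so it is arguable whether that rule applies to them.

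One smaller gap remains. The SAP 3.4 outcome on AE frequency up to 7 days includes transfusion-related events, but 7.8.1 has no row for them. Protocol 7.1 requires categorisation against several sources but does not say that this yields a transfusion-related flag, so whether a row is feasible cannot be settled from the text.

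**What to change.** 1. In protocol 13.2, the synopsis and SAP 5.1, delete the low-rate reason. Suggested wording: *The sample size was not chosen on statistical criteria. If 10 patients per group (20 in total) are transfused, an event with a true per-patient rate of 14.9% within a group (7.7% overall) has an 80% chance of being seen at least once. If none is seen, the two-sided 95% upper limit is 30.8% within a group (16.8% overall).*
2. In SAP 7.8.1 and 7.8.2, add exact Clopper-Pearson 95% intervals for the 24-hour and 7-day AE and ADE proportions, by group and in total. Name the safety analysis set (SAP 7.2.2), use its actual number, and show the interval at zero counts as an exception to SAP 7.1.1.
3. State that the intervals are descriptive and test no hypothesis. This keeps them consistent with the synopsis, with protocol 13.4.2, and with 13.4.3, which says "The analysis of quantitative secondary endpoints will be limited to descriptive statistics".
4. Add a row for transfusion-related AEs to SAP 7.8.1 if the categorisation under protocol 7.1, as collected, allows them to be identified. If it does not, say so in the SAP.

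Separately, reconcile protocol 9.4 with 13.5, which mentions replacement only for those who drop out before transfusion.

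**Cost.** Wording changes, with a protocol amendment for the protocol text; one interval column in two tables; one conditional row. No extra patients. The stated case for twenty becomes less favourable.

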13.3 Statistical criteria of termination of the investigation

There are no statistical criteria for the termination of the investigation.

13.4 Planned Analyses

A descriptive analysis will be performed on all quantitative data: means and standard deviations will be calculated for quantitative data, medians and interquartile intervals for discrete data, performance and qualitative variables. A listing of all AEs will be provided.

13.4.1 Datasets to be analysed, analysis populations

Data from all patients will be included in the analysis. This includes data from patients who withdraw or drop out of the study up to and including their last visit.

13.4.2 Primary Analysis

This clinical investigation is not powered to support a quantitative analysis of the primary endpoint.

13.4.3 Secondary Analyses

The analysis of quantitative secondary endpoints will be limited to descriptive statistics.

13.4.4 Interim analyses

There will be no interim analysis of the study endpoints.

13.4.5 Deviation(s) from the original statistical plan

All deviations from the statistical plan will be reported and if necessary the statistical plan will be updated.

13.5 Handling of missing data and drop-outs

Investigators will attempt to contact any patients who received a transfusion during the investigation and who subsequently dropped out of the study in order to ensure that they did not experience any adverse events either in the 7 days (+/- 1) following their transfusion, or beyond 7 days (+/-1) until their following transfusion or 28 days post-transfusion, whichever comes first. Any patients who drop out of the investigation before receiving a transfusion will be replaced in order to meet the sample size requirements.

14. QUALITY ASSURANCE AND CONTROL

All participant data relating to the study will be recorded on printed or electronic CRF unless transmitted to the sponsor or designee electronically (eg, laboratory data). The investigator is responsible for verifying that data entries are accurate and correct by physically or electronically signing the CRF. The investigator must maintain accurate documentation (source data) that supports the information entered in the CRF.

The investigator must ensure that the CRFs are securely stored at the study site in encrypted electronic and/or paper form and are password protected or secured in a locked room to prevent access by unauthorized third parties.

The investigator must permit study related monitoring, audits, ethics committee review, and regulatory agency inspections and provide direct access to source data documents. This verification may also occur after study completion. It is important that the investigator(s) and their relevant personnel are available during the monitoring visits and possible audits or inspections and that sufficient time is devoted to the process.

Monitoring details describing strategy, methods, responsibilities, and requirements, including handling of noncompliance issues and monitoring techniques, are provided in the monitoring plan.

The sponsor or designee is responsible for the data management of this study, including quality checking of the data.

Study monitors will perform ongoing source data verification to confirm that data entered into the CRF by authorized site personnel are accurate, complete, and verifiable from source documents; that the safety and rights of participants are being protected; and that the study is being conducted in accordance with the currently approved protocol and any other study agreements, ISO 14155:2020, ICH GCP, and all applicable regulatory requirements.

The investigator(s) will notify the sponsor immediately of any regulatory inspection notification in relation to the study. Furthermore, the investigator will cooperate with the sponsor to prepare the investigator site for the inspection and will allow the sponsor, whenever feasible, to be present during the inspection. The investigator site and investigator will promptly resolve any discrepancies that are identified between the study data and the participant's medical records. The investigator will promptly provide copies of the inspection findings to the sponsor or its agent. Before response submission to the regulatory authorities, the investigator will provide the sponsor or its agents with an opportunity to review and comment on responses to any such findings.

14.1 Data handling and record keeping / archiving

Records and documents pertaining to the conduct of this study must be retained by the investigator for 15 years after study completion unless local regulations or institutional policies require a longer retention period. No records may be destroyed during the retention period without the written approval of the sponsor. No records may be transferred to another location or party without written notification to the sponsor. The investigator must ensure that the records continue to be stored securely for as long as they are maintained.

When participant data are to be deleted, the investigator will ensure that all copies of such data are promptly and irrevocably deleted from all systems.

14.1.1 Case Report Forms

All original source data will be contained in original laboratory printouts, site laboratory notebooks, site data sheets and/or study-specific source documents. Data transmittal to the Sponsor will be accomplished using paper Case Report Forms (CRFs). Original source data will not be entered directly on the CRFs. Original data is to be transcribed from source data records to the CRFs by site study staff. Data entered onto the CRFs will then be verified against the source data during Sponsor on-site monitoring visits. At the study site visits the verified and corrected CRFs must be reviewed and

electronically signed by the respective Principal Investigator to finalize the data. Investigative site study data and records for this protocol are subject to monitoring or inspection by the Sponsor, and notified body.

